6.1 Anticipated Toxicities

A list of the adverse events and potential risks associated with the agents administered in this study appear below and will determine whether dose delays and modifications will be made or whether the event requires expedited reporting **in addition** to routine reporting.

Acute side effect assessment should include the following:

- Anorexia
- Nausea + vomiting (esp. with vincristine)
- Weight loss
- Fatigue
- Headache
- Skin reactions
- Alopecia (total alopecia expected)
- Thrush (fungal infection of the mouth)
- Sore throat or esophagitis
- Decrease in bone marrow cells
- Constipation (esp. with vincristine)

Any of the above may lead to a need for treatment break or delay in finishing treatments.

Non-physical Risks:

- Inability to perform at school or job

Patient monitoring should be done per usual clinical practice.

Late Effects:

- Permanent hair loss or thinning in region of boost
- Decreased growth overall (GH effects)
- Decreased growth of spine
- Hormonal imbalance
- Hearing impairment
- Neurocognitive effects
- Cataracts
- Hypothyroidism
- Neuroendocrine effects, may lead to an inability to have children
- Abnormal curvature of the spine
- Scarring or damage to the esophagus
- Damage to the spinal cord or brain tissue
- Tumors caused by radiation
- Vascular effects, either asymptomatic or causing stroke

6.2 Toxicity Management

Toxicity that causes a delay or dose modification in radiation therapy is not expected. Once radiation has started it is important to continue with radiation unless it is deemed unsafe for the patient (i.e. they require anesthesia and have pneumonia). If the patient experiences toxicity from chemotherapy, delays and dose modifications should be made according to the concurrent chemotherapy treatment protocol.

6.3 Dose Modifications/Delays

To avoid treatment delays resulting from the proton machine being down, photon beam radiation can be administered. The maximum dose for both the posterior fossa and spine will be 20% of the dose (e.g. 20% of the spine at 36 Gy would be a max. of 4 spine treatments). Delay in the start of CSI proton therapy treatment should not exceed 2 weeks in M0 patients and 1 week in M+ patients.

Radiation treatment delays must be avoided where possible. If a patient is unable to receive a CSI treatment on a given day then consideration should be made to delivering the boost treatment where possible.

7. DRUG FORMULATION AND ADMINISTRATION: N/A

8. CORRELATIVE/SPECIAL STUDIES: N/A

9. STUDY CALENDAR

Baseline evaluations are to be conducted within 35 days prior to start of protocol therapy. Scans must be performed within 6 weeks prior to the start of therapy. CSF sampling can be completed any time prior to start of protocol therapy.

Table 2: Required Data

Tests and Observations	Pre-Study/ Baseline	During Radiation	Follow Up (1)
Informed Consent and registration	X		
Biopsy or attempted resection	X		
Pathology Review	X		
Medical History	X		X (2)
Physical Exam	X	X (2)	X (2)
Endocrine Evaluation	X (3)		X (3)
CSF sampling if M0 disease	X (4)		
CBC	X (5)		X (5)
Serum Chemistries	X (6)		X (6)
MRI or CT of the brain	X (7)		X (7)
MRI of the entire spine	X (8)		X (8)
Audiogram	X (9)	X (9)	X (9)
Neurocognitive Testing	X (10)		X (10)

Notes:

(1) Follow up, except for neurocognitive testing, is to be completed annually (+ or – 6 months) from the completion of study treatment. Follow up is highly recommended, but not required.

(2) Medical history and physical exams during radiation treatment is to be completed weekly and may include only the acute toxicity assessment and other pertinent objective findings. Medical history and physical exams at follow up are recommended, but not required.

(3) Baseline endocrine evaluation to be completed no later than 2 months after the start of radiation. Evaluation includes Tanner stage assessment by physical exam, bone age (plain film of the wrist), and body proportion measurements. Bone age, Tanner Stage assessment, and body proportion measurements collected will be at the discretion of the study endocrinologist. Recommended measurements include sitting height (sitting height preferred, but pubic symphysis to floor acceptable), standing height, leg span, and arm span. Recommended labs for endocrine evaluation are TSH, Free T4, Cortisol, IGF-1, IGF-BP3, LH, FSH, estradiol (females) and testosterone (males) – am levels preferred,

(4) CSF sampling can be done any time prior to the start of protocol therapy. CSF sampling must be completed no later than ten days after the start of radiation. If sampling performed less than 10 days after surgery is positive, it should be repeated.

(5) CBC required labs are ANC, Platelets, Hematocrit. CBC with diff. is required at baseline. Annual follow up CBC's are suggested, but not required

(6) Chemistries required at baseline and that are suggested, but not required, for follow up are: albumin, alk phos, T bili, BUN, calcium, chloride, glucose, potassium, total protein, sodium, AST, ALT, Pregnancy test (if applicable and at pre-study only).

(7) Pre-Study brain MRI or CT includes pre-op and post-op imaging, post-op to be done within 21 days of surgery (preferably within 72 hours of surgery; intra-operative MRI as allowed). Brain MRI or CT at follow up is recommended, but not required.

(8) Pre-study spine MRI should be from the time of diagnosis (preferably pre-op). Spine MRI at follow up is recommended, but not required.

(9) Baseline audiogram must be completed within 2 months after the start of radiation. Audiograms are recommended, but not required, for patients receiving platinum based chemotherapy prior to the beginning of each cycle. Follow up audiograms are recommended annually. Additional audiograms, if done, will be collected and included in the data set.

(10) Baseline neurocognitive testing must be completed no later than 9 months after the start of radiation. Follow up testing is recommended starting one year after the previous exam, at one, three, and five years post-radiation (+ or – 12 months).

Patient Assessments:

The required tests and evaluations prior to, during and following CSI are shown in table 2. Patients will require acute side effect assessment during radiation therapy as detailed in section 9.1 below. Acute side effects from RT are defined as those effects that are attributable to the effects of radiation and occur from commencement of RT to 90 days following completion of RT.

Patients will be assessed for late side effects or complications which are defined as those effects that are attributable to the effects of radiation and occur > 90 days following completion of RT.

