9.2.2 Audiology evaluation

Audiograms are required and should be done prior to start of radiation. Audiograms should be obtained on a yearly basis as well (see table 2). Additionally regular audiograms are recommended but not required to be performed at the patient's home institution prior to each cycle of platinum based chemotherapy in accordance with the standard of care because platinum chemotherapy can cause acute hearing loss. If the baseline audiogram cannot be completed prior to the start of radiation, it must be completed within 2 months of the beginning of radiation therapy. Each ear (left and right) should be tested and recorded separately.

Grading of sensorineural hearing loss will be according to the CTEP Active Version of CTCAE.

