14.1 Study Design/Endpoints

Accrual goals are 60 standard-risk and 30 high-risk patients. In the pediatric MB population treated with conventional photon CSI, 3-year progression-free survival of standard-risk patients is in the 75-80% range depending on the concurrent use of chemotherapy, while 65-70% is reported among high-risk patients. Thus, 48 standard-risk and 20 high-risk patients are projected to be evaluable for late complications at 3 years following the CSI completion; patients who progress or die sooner will not contribute in the analysis of late complications.

The primary endpoint of ototoxicity at 3 years following completion of radiation therapy will be based on failure events defined by grade 3 or 4 sensorineural hearing loss (SNHL) according to COG criteria. They include progressive hearing decrease to grade 3 or 4 following mild or moderate loss (grade 1 or 2) typically experienced during platinum-based chemotherapy. All patients who have audiology assessments prior to censorship will contribute to the actuarial analysis. Patients will be censored in the event of death, drop out or progression of disease. The historical rates of late SNHL is in the 50% range among pediatric MB patients [9, 10] treated with conventional CSI and cisplatin-based chemotherapy. We shall conclude proton therapy leads to an improvement in the high-risk group if 7 or fewer of 20 patients were to experience grade 3 or 4 SNHL at 3 years following completion of radiation therapy. The decision rule is associated with 77% power if the SNHL rate were truly reduced to 30% among the high-risk patients. In contrast, the probability is only 13% for concluding incorrectly an improvement if the underlying SNHL rate were 50%. In the null hypothesis for the standard-risk group, we assume conventional CSI and cisplatin-based chemotherapy is associated with an SNHL rate less than 50% due to their lower CSI dose, in particular, 40%. We shall conclude proton therapy leads to an improvement in the standard-risk group if 14 or fewer of 48 patients were to experience grade 3 or 4 SNHL at 3 years following completion of radiation therapy. The decision rule is associated with 80% power if the SNHL rate were truly reduced to 25% among the standard-risk patients. In contrast, the probability is only 8% for concluding incorrectly an improvement if the underlying SNHL rate were 40%.

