14.2 Sample Size/Accrual Rate

Based on recent clinical experience, the protocol is projected to accrue about 18 patients per year combined between the two participating institutions. Enrollment is planned for 5 years in order to meet the overall accrual goal of 90 patients. The observed risk distribution of MB and PB patients has been approximately a 2:1 ratio so that 60 standard-risk and 30 high-risk patients will be accrued for the sample size requirements. A minimum follow up of 3 years is required for observing the late complications of proton beam irradiation.

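### The 3-year hearing decision uses fixed counts that hold only at exactly 48 and 20 assessed patients, while the follow-up audiograms behind it are optional

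*Combined protocol and SAP*

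**What the plan says.** **Whether the audiogram is needed.** Table 2 (section 9) marks an audiogram at follow-up. Its note 1 sets annual follow-up with a window of 6 months either side, and then says "Follow up is highly recommended, but not required". Note 9 says "Follow up audiograms are recommended annually". Section 9.2.2 is a little firmer, "Audiograms should be obtained on a yearly basis as well", and sends the reader to Table 2. Section 14.2 says "A minimum follow up of 3 years is required for observing the late complications". Section 5.6 invites patients back each year and lets those living elsewhere have follow-up at home and send in the records.

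**The decision rule.** In section 14.1, "Accrual goals are 60 standard-risk and 30 high-risk patients". The section notes that "3-year progression-free survival of standard-risk patients is in the 75-80% range" and that "65-70% is reported among high-risk patients", and from these it projects 48 and 20 patients evaluable at 3 years. The only losses named in that projection are progression and death. Improvement is concluded if at most 14 of 48 standard-risk patients, or at most 7 of 20 high-risk patients, have grade 3 or 4 sensorineural hearing loss (SNHL) at 3 years. Stated error and power are 8% and 80% for standard risk (40% against 25%), and 13% and 77% for high risk (50% against 30%).

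**The analysis.** Sections 14.1 and 14.4 also plan an actuarial estimate, primarily at 3 years. Patients with any audiology before censoring contribute, and those who progress, die, drop out or are lost are censored.

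**The concern.** A count rule has a known error rate only for a known denominator. Here the denominator depends on a test that sites may omit without departing from Table 2, and the planning figure leaves no room for that. It also depends on progression-free survival reaching the best value quoted for standard risk.

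If fewer patients are assessed, the plan does not say what happens to the cut-off. Keeping 14 and 7 makes the rule easier to pass, so the risk is a false conclusion that protons reduce hearing loss. Tightening the cut-off to hold the error means that the stated power is not delivered. The actuarial estimate could resolve this, but no passage says how a 3-year actuarial rate is compared with 14 of 48 or 7 of 20. An analyst would have to choose after seeing the data.

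**Working it through.** **Inputs (section 14.1).** Accrual is 60 and 30. Three-year progression-free survival is 75-80% and 65-70%. The rules are c = 14 of n = 48 (p0 = 0.40, p1 = 0.25) and c = 7 of n = 20 (p0 = 0.50, p1 = 0.30). The documents give no rate of missing audiograms; 10-20% below is an assumption.

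**Formula.** P(X ≤ c) = Σ C(n,k) p^k (1−p)^(n−k), summed over k = 0 to c. This is the error at p0 and the power at p1.

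**Step 1: the plan's own figures.**
- 14 of 48: error 8.13%, power 80.0%.
- 7 of 20: error 13.16%, power 77.2%.

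All four match section 14.1 to rounding, with every one of the 48 and 20 patients assessed.

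**Step 2: where the denominators come from.**
- Standard risk: 60 × 0.80 = 48; 60 × 0.75 = 45.
- High risk: 30 × 0.65 = 19.5; 30 × 0.70 = 21; 20/30 = 66.7%.

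So 48 is the top of its range, while 20 lies inside its range.

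**Step 3: low end of the survival range, no audiogram missing (n = 45).** This uses only the protocol's own figures.
- Cut-off 14: error 14.3%, power 86.7%.
- Cut-off 13: error 8.4%, power 78.4%.
- Cut-off 12: error 4.5%, power 67.5%. This is the largest cut-off that does not exceed 8.13%.

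**Step 4: 10-20% of audiograms missing from 48 and 20 (assumed).** Evaluable numbers are 48 × 0.90 = 43.2, 48 × 0.85 = 40.8 and 48 × 0.80 = 38.4, taken as 43, 41 and 38; and 20 × 0.90 = 18, 20 × 0.85 = 17 and 20 × 0.80 = 16.

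| Group | Missing | n | Printed count kept: error | Largest cut-off within original error | Its error / power |
|---|---|---|---|---|---|
| Standard | 10% | 43 | 20.1% | 12 | 7.0% / 73.7% |
| Standard | 15% | 41 | 27.5% | 11 | 5.7% / 68.2% |
| Standard | 20% | 38 | 41.3% | 10 | 5.7% / 65.6% |
| High | 10% | 18 | 24.0% | 6 | 11.9% / 72.2% |
| High | 15% | 17 | 31.5% | 5 | 7.2% / 59.7% |
| High | 20% | 16 | 40.2% | 5 | 10.5% / 66.0% |

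Power does not fall smoothly because the cut-off moves in whole patients.

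**Step 5: cut-off scaled in proportion instead.** The printed rules are 14/48 = 29.2% and 7/20 = 35.0%. At 15% missing the nearest equivalents are 12/41 = 29.3% and 6/17 = 35.3%:
- 12 of 41: error 10.5%, power about 79%.
- 6 of 17: error 16.6%, power about 78%.

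The same shortfall therefore gives standard-risk error of 27.5%, 10.5% or 5.7%, depending on a choice that the plan leaves open.

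**The case against.** The strongest reply is that the plan already handles incomplete follow-up. The actuarial analysis keeps a patient with audiograms at years 1 and 2 but none at year 3, so a missed 3-year test does not simply delete a patient. Section 2.3 describes late effects as tending to be permanent, so a later audiogram without grade 3 or 4 loss would usually settle the 3-year status too. This stands for estimation, and it means that the reduced denominators in step 4 overstate the loss of information. It does not settle the decision, because the rule is written as counts and never tied to the actuarial estimate. Censoring for a skipped optional test is also unbiased only if skipping is unrelated to hearing, which the plan neither states nor checks.

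Three stronger readings are tempting, and the documents do not support them.

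- A reader might infer that the documents flatly contradict each other on whether the audiogram is mandatory. The wording in 9.2.2 is firmer than Table 2 but is not a mandate. Section 14.2 can be read as a maturity requirement for the analysis rather than a test owed by each patient. The passages need aligning; they do not clash outright.
- A reader might infer that the trial will run at 20-41% error. That requires someone to keep 14 or 7 after the denominator has shrunk, although the rules are stated out of 48 and out of 20. With proportional scaling the drift is 2-3 points and power is nearly unchanged.
- A reader might infer that both denominators are optimistic. Only the 48 is.

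It is also fair to say that recommending rather than requiring a test can be a defensible choice in a single-arm phase II trial whose stated objective is estimation, and that writing in a requirement does not guarantee data.

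**Conclusion.** The point holds as a gap in the decision rule and should be fixed; it does not invalidate the design. The stated error and power are correct, but only for 48 and 20 assessed patients. The follow-up audiograms behind those numbers are optional, no missing tests are allowed for, and no rule covers any other denominator or links to the actuarial estimate.

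The firmest evidence is the 45-patient case, which needs no outside assumption: 14.3% error if the count is kept, or 8.4% error and 78% power with a cut-off of 13. That is a modest change if the cut-off is adjusted and a material one if it is not. The larger figures depend on the assumed 10-20% missing rate, on treating a patient without a 3-year audiogram as not evaluable, and on how the cut-off is handled.

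**What to change.** 1. **Table 2 notes 1 and 9, and section 9.2.2.** State consistently that the 3-year audiogram is required for patients alive without progression, within the existing window of 6 months either side. Local records may be forwarded, as section 5.6 already allows.
2. **Section 14.1, the rule.** Replace the two fixed counts with a rule set in advance for the number actually evaluable, and say which analysis it applies to. There are two options:
   - a cut-off table whose error does not exceed the original exact values, 8.13% and 13.16%. The exact values matter: ceilings rounded to 8% and 13% would reject the protocol's own 14 of 48 and 7 of 20, which should be kept at full numbers;
   - a confidence bound on the 3-year actuarial estimate, which makes use of partial follow-up.
3. **Section 14.1, the planning figures.** Restate error and power for 45-48 standard-risk and 19-21 high-risk patients, with a range of missing audiograms marked as an assumption.

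No new procedure is added, since annual audiograms are already in the calendar. The costs are some follow-up effort, deviations to record when the test is missed, and less favourable stated power. Under the cut-off table, 12 of 45 has 67.5% power and 6 of 19 has 66.6%.

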2.3 Rationale

The treatment of MB and PB of the central nervous system involves a multi-disciplinary approach. Surgery is necessary to obtain histological confirmation and to obtain maximal resection of tumor when feasible as the degree of resection correlates with outcome [4]. Patients are at risk for local and disseminated CNS recurrence even after gross total resection. Adjuvant therapy to the craniospinal axis is therefore essential. Craniospinal irradiation (CSI) is used in this setting for patients greater than 3 years of age. An additional boost of radiation encompassing the residual tumor and surgical bed is routinely given as this region is at highest risk for recurrence.

Photon CSI is associated with many possible acute and long-term sequelae:

Acute toxicity can include the following: bone marrow myelosuppression, fatigue, alopecia, headache, dermatitis, folliculitis, otitis externa, otitis media, anorexia, weight loss, nausea, vomiting, thrush, laryngitis, pharyngitis, esophagitis, gastritis, enteritis, cystitis, acute pericarditis, and temporary worsening of tumor associated neurological symptoms.

Prolonged myelosuppression and decreased bone marrow reserve may limit the ability to give chemotherapy after CSI. Somnolence syndrome is a subacute reaction associated with CSI often disabling the patient.

Long-term complications typically occur 3 months or more following completion of photon CSI and tend to be permanent. Complications arising from irradiation of the cranium include induction of second malignancy, permanent hair loss, cataract formation, retinopathy, sensorineural hearing loss due to damage to cochlea apparatus in inner ear, neuroendocrine dysfunction, and neuro-cognitive sequelae, rarely, necrosis and associated persistent vasogenic edema or atrophy. Adverse long term effects from photon irradiation of the spinal axis include: induction of second malignancy, stunting of growth of vertebral bodies and hypoplasia of paraspinal muscles and connective tissue resulting in scoliosis, kyphosis and decreased stature, spinal cord or nerve root damage, primary hypothyroidism, cardiomyopathy, pneumonitis, peptic ulcer disease, small and large bowel enteritis, primary ovarian failure, and decreased marrow reserve. These long-term sequelae can have

devastating effects in children on their future development and quality of life. Some of these complications are described in further detail below.

Ototoxicity:

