11.2 Definitions

11.2.1 Adverse Event (AE)

An adverse event is any undesirable sign, symptom or medical condition or experience that develops or worsens in severity after starting the first dose of study treatment or any procedure specified in the protocol, even if the event is not considered to be related to the study.

Abnormal laboratory values or diagnostic test results constitute adverse events only if they induce clinical signs or symptoms or require treatment or further diagnostic tests.

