14.4 Analysis of Endpoints

Progression-free survival is measured from the start of radiation therapy to the date of documented disease progression or death in the absence of progression. Patients who have not progressed or died will be censored at the time of last follow up. Progression-free survival will be estimated by the Kaplan-Meier method. Acute effects will be summarized according to specific events with exact 95% confidence intervals for binary data. The incidence of late complications will be based on actuarial estimates, primarily at 3 years. Patients who die, progress, or are lost to follow up prior to 3 years will be censored. Other factors which may influence late complications will be explored in multivariate models, including gender, age, radiation dose to the posterior fossa, dose volume histogram of the normal tissue as well as drugs, dosages and sequencing of the chemotherapy regimen. In addition, we shall control for pre-existing hearing deficits in the analysis of ototoxicity, while methotrexate usage will be of interest in the analysis of neurocognitive functioning among high-risk patients. Multivariate analyses will be primarily exploratory due to the modest patient numbers in each risk group.

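### Reduced marrow counts are on the acute-effects list, but no blood count is scheduled in the acute window, so ascertainment depends on local practice and probably under-counts

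*Combined protocol and SAP*

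**What the plan says.** Section 6.1 names "Decrease in bone marrow cells" among the items that acute assessment should cover, and leaves patient monitoring to usual practice. Section 9.1 requires weekly acute toxicity assessment during CSI, graded by CTCAE. Section 9 defines acute effects as radiation effects that "occur from commencement of RT to 90 days following completion of RT".

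Table 2, which sets out the required data, marks CBC at baseline and at follow-up and has nothing under radiation. Note (5) confirms this: "CBC with diff. is required at baseline. Annual follow up CBC's are suggested, but not required". Note (1) says that follow-up other than neurocognitive testing "is to be completed annually (+ or – 6 months) from the completion of study treatment", and that it is recommended rather than compulsory.

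Section 11.2.1 limits when a laboratory abnormality is an adverse event: "only if they induce clinical signs or symptoms or require treatment or further diagnostic tests". Sections 11.1 and 11.3 send adverse events, including those found by laboratory test, to the case report forms.

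On analysis, section 14.4 states: "Acute effects will be summarized according to specific events with exact 95% confidence intervals for binary data".

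**The concern.** A marrow grade needs a blood count. The plan asks for the grade but schedules no count in the period when it applies, and its adverse event definition lets some gradable counts drop out even when a site has taken them. Whether a given cytopenia appears in the data then depends on how often the site draws blood and how it reads section 11.2.1.

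The protocol itself treats this effect as important. Section 1 sets out to describe acute as well as late complications, and section 2.3 warns: "Prolonged myelosuppression and decreased bone marrow reserve may limit the ability to give chemotherapy after CSI". If marrow toxicity is reported under section 14.4, its exact interval will allow for sampling error only and cannot correct for cases that were never counted. Section 14.5.1 makes every participant evaluable for toxicity from first treatment. Unless the analysis says otherwise, a patient with no recorded count would therefore stay in the denominator as a non-event.

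**Working it through.** **1. Scheduled counts inside the acute window.** The inputs are Table 2 with notes (1) and (5), and the definition of acute effects in section 9.
- Baseline evaluations are done in the 35 days before therapy, so the baseline count precedes the window.
- During radiation: no CBC is marked. The weekly visit in note (2) may be confined to toxicity assessment and pertinent objective findings, and no laboratory test is named.
- After radiation: the earliest in-window annual visit is 12 − 6 = 6 months, about 183 days. The window closes at day 90, so that visit comes about 183 − 90 = 93 days too late, and its CBC is optional.
- Scheduled CBCs in the window: 0.

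**2. Which unscheduled counts reach the data.** Section 11.2.1 set beside section 9.1:

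| Low count found in routine care | Gradable by CTCAE (9.1) | Adverse event (11.2.1) |
|---|---|---|
| Causes signs or symptoms | Yes | Yes |
| No symptoms, but treated | Yes | Yes |
| No symptoms, but further tests needed | Yes | Yes |
| None of these; watched until it recovers | Yes | No |

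The last row is the gap. Its edge is also unclear: the protocol does not say whether a repeat CBC is a further diagnostic test, so two sites could classify the same event differently. Table 2 note (9) closes the equivalent gap for hearing by taking any additional audiograms into the data set. Note (5) has no such sentence.

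**3. The plan's own precision figures.** The plan gives no figure for marrow toxicity. The nearest are the exact 95% interval widths in section 14.1, which it expects to be narrower for acute effects. With x events in n patients, the lower limit is the 2.5% quantile of Beta(x, n − x + 1) and the upper limit is the 97.5% quantile of Beta(x + 1, n − x). The maximum width over all x is:
- n = 48: 29.5% (plan: under 30%)
- n = 20: 45.6% (plan: 46%)

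Both reproduce. At full accrual the widths are 26.4% (n = 60) and 37.4% (n = 30), so acute effects would indeed have narrower intervals.

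**4. What incomplete capture does to such an interval.** If the true rate is p and a fraction f of cases is recorded, the expected observed rate is p × f. The documents give neither value. As an illustration only, assume p = 50% and n = 60, rounding to whole patients:

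| Fraction captured | Events recorded | Observed rate | Exact 95% interval |
|---|---|---|---|
| 100% | 30 | 50.0% | 36.8–63.2% |
| 75% | 22 | 36.7% | 24.6–50.1% |
| 50% | 15 | 25.0% | 14.7–37.9% |
| 25% | 8 | 13.3% | 5.9–24.6% |

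At half capture the interval excludes the assumed true rate. With n = 30 and half capture, 8 events give 26.7% (12.3–45.9%), which also excludes it. The table shows the mechanism; it does not estimate this trial's loss.

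**The case against.** The best reply is that the protocol already has a route for these data. Section 6.1 specifically names marrow suppression, section 9.1 grades it weekly, section 11.1 accepts events found by laboratory test, and section 11.3 puts all adverse events on the forms. A site could take the specific instruction in 6.1 to prevail over the general definition in 11.2.1. The case report forms, and the submission schedule that section 12.1.2 places in Appendix A, are not in the text available, so the toxicity form may have fields for counts. Acute effects are also only a secondary objective: 1.3.3 gives nausea, esophagitis and weight loss as examples and does not mention marrow, although its list is open.

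Much of this stands, and it rules out some stronger readings that a reader might infer:
- **That 11.2.1 excludes every symptom-free abnormal result.** It does not; treatment or further testing is enough to qualify.
- **That the exemption of grade 4 myelosuppression from prompt reporting (11.4, 11.4.1) means such events leave no record.** Those sections govern expedited reporting, not entry on the forms.
- **That marrow is always in the target.** Section 5.2.3 leaves inclusion of the vertebral body to the treating physician and only recommends covering it in patients with much growth remaining.

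The reply does not supply a count inside the window, or say which of 6.1 and 11.2.1 governs an untreated, symptom-free low count.

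**Conclusion.** The point holds as a gap between sections 6.1 and 9.1, Table 2 and section 11.2.1. An effect listed for assessment and grading has zero scheduled measurements in its window, and some gradable counts fall outside the adverse event definition. Ascertainment will vary with local practice and will probably miss mild or untreated cytopenia. The direction rests on one assumption: that missed cases outnumber any wrongly recorded ones.

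It would be tempting to say that acute marrow toxicity will go largely unrecorded, or that the reported rate will be false for all 90 patients. The documents do not support that. They give no capture fraction, and routine counts can reach the forms. The schedule gap applies to everyone; the loss of data cannot be quantified.

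The consequence is confined to a descriptive, secondary result. The late-effect endpoints, the accrual goals of 60 and 30, and the hearing-loss decision rules do not use these counts.

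**What to change.** Add to Table 2 note (5) a sentence modelled on note (9): CBCs obtained in routine care from the start of radiation to 90 days after its end will be collected. Then:
- record the lowest ANC, platelets and hematocrit in that period, with dates, and the chemotherapy given in it;
- grade these by CTCAE whether or not the patient had symptoms, as a stated exception to section 11.2.1;
- report grade 3-4 rates by risk group and concurrent chemotherapy, with the number of patients who had any count.

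If the sponsor does not want these data, the alternative is to state that acute marrow toxicity will not be estimated.

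The cost is a footnote, a short form entry, modest data entry and retrieval of outside laboratory reports. Section 5 already asks for chemotherapy documentation. No blood draw or clinical rule changes. The limitation is that timing still follows local practice, so some lowest values will be missed, and separating radiation from chemotherapy effects will remain uncertain.
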